MRI can detect soft tissue and bone inflammation of hip. There was a recent Chinese study investigating inflammatory MRI changes in AS patients investigating pattern of hip involvement. Active inflammatory changes included subchondral bone marrow edema, joint effusion, abnormal synovial enhancement, enthesitis at sites where ligaments and tendons are attached to bone. They are visualized

Product: MK-8259

Protocol/Amendment No.: 021

VEAP ID NO: 6189

Date: 15-January-2018

best by STIR (short tau inversion recovery) sequence and fat-saturated contrast-enhanced T1-weighted sequence. Chronic inflammatory changes were fatty degeneration, erosive destruction, joint space narrowing, sclerosis, ankylosis. They are best seen by using a T1-weighted TSE sequence [10]. The proportion of hip involvement according to MR imaging, radiographs, and clinical symptoms was:

	Proportion of hip involvement
MRI	74,1% (86/116)
Radiography	20,7% (24/116)
Clinical symptoms	30,2% (35/116)

MRI yielded higher values than radiographs and clinical symptoms in the detection of hip involvement in patients with AS ($P <0.05$). The frequency of MRI changes in 81 hips (42 patients) have been shown to be: acute changes alone – 43,1%, chronic and acute changes – 26,7%, normal – 25,9%, chronic changes – 4,3%. The rates of acute MRI inflammatory changes have been shown to be:

	Rates of acute MRI inflammatory changes
Synovitis alone	48,1%
Synovitis + bone edema	21,0%
Synovitis + bone edema + enthesitis	18,5%
Synovitis + enthesitis	8,6%
Bone edema alone	3,7%
Enthesitis alone	0
Bone edema and enthesitis	0

There are no studies investigating correlation of different radiological manifestations over time.

According to current international guidelines, management of AS patients with coxitis does not differ from management of AS patients without hip involvement and includes physiotherapy, pharmacological therapy (NSAIDs, sulfasalazine, TNF alpha inhibitors) and surgery [8,11,12,13]. The latter is total hip replacement which is used in cases of end-stage disease [9]. In analysis of three databases of AS patients (Belgian database ASPECT, n=847, Spanish database REGISPOSNER, n=1405 and Ibero-American database RESPONDIA, n=466), it was shown that 5-8% of the AS patients undergo hip replacement surgery, 47% of them have bilateral hip replacement. After >30 years of disease duration, the chance of having at least one replaced hip is 12-25% [4]. Investigators who were analyzing Norwegian

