Product: MK-8259

Protocol/Amendment No.: 021

VEAP ID NO: 6189

Date: 15-January-2018

Arthroplasty Register noticed that in 2003-2010 there was a trend towards a reduced frequency of hip replacement procedures in the AS group when compared to osteoarthritis group. It was hypothesized that this trend was related to broader introduction of TNF alpha inhibitors [14].

According to the ASAS/EULAR recommendations for the management of ankylosing spondylitis, anti-TNF therapy should be given to patients with persistently high disease activity despite conventional treatments [11]. Literature search identifies three publications on efficacy of TNF alpha inhibitors in hip disease in AS patients.

The first one, by Wang D. et al, describes results of follow-up in 56 patients with AS with coxitis treated with etanercept in combination with MTX. It was shown that Harris hip score, BASDAI, BASFI, ESR, CRP improved after 12 weeks of therapy ($p<0,001$ for all measurements). No radiological data were provided [15].

The second one, by Lian F. et al, presents results of 12-month treatment of coxitis in 92 AS patients with etanercept in combination with MTX. It was shown that Harris hip score, BASDAI, BASFI, ESR, CRP improved after 12 months of therapy ($p<0,05$ for all measurements). In the whole population of patients BASRI-hip remained with no changes (baseline vs. 12 month of treatment). MRI proved a total of 93 hip joints (51%) had joint fluid synovitis in MRI at baseline and 13 positive hip joint fluid synovitis at the 12th month [16]. Other MRI symptoms were not described by the authors.

The third one, by Konsta M. et al, contains results of retrospective study analyzing clinical (BASDAI, BASFI) and radiographical (BASRI hip, mean joint space width) in 23 patients being treated with infliximab for $6\pm2,5$ years (mean \pm SD). BASDAI and BASFI improved over time (from 6.3 and 6.9 to 1.67 and 3.3, respectively), while individual BASRI-hip scores at baseline (2.50 ± 0.86 , mean \pm SD) remained unchanged as well as the average width of the whole joint space in these patients (3.59 ± 0.79 mm) was not reduced at end of follow-up. Authors assume that TNF inhibitors are able to inhibit structural progression of hip disease in AS but state that prospective studies with at least 2-years follow-up are required to investigate structural progression of coxitis in AS [17].

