1.2 Rationale

Coxitis in AS is inflammation of hip(s) affecting significant number of patients. It is associated with worse function and more expressed axial disease requiring hip replacement at end-stage. Clinical symptoms (pain and affected movement) should be confirmed with imaging (X-ray and MRI). Synovitis and its combination with bone edema and enthesitis are the most frequent MRI manifestations. There are no data on change of these manifestations over time with or without treatment. US imaging can reveal inflammatory changes in hips but there are no data on change of US manifestations over time.

Number of studies dedicated to coxitis treated with TNF alpha inhibitors is very limited: one of them is a retrospective study with 23 patients, two others are prospective but with short follow-up for 12 months (when at least two years are recommended as a follow-up in AS to investigate the radiographic progression) and without conclusive imaging data (MRI and/or US). Simponi® (golimumab) has not been studied in hip disease in AS although it is registered for AS.

Hip disease in ankylosing spondylitis is understudied. This study will provide valuable data on clinical and radiological signs of coxitis in AS at baseline and its clinical and radiological evolution during treatment with TNF alpha inhibitors in daily clinical practice. Collection of radiological data will include US and MRI which have not been widely explored as evaluation of coxitis in AS in previous studies.

Based on data from studies described in the Background section it can be expected that the TNF alpha inhibitor golimumab will be effective clinically and radiologically:

- 1) it is expected significant improvement of BASFI at 12 months from the baseline;
- 2) it is expected that there will be no structural progression of coxitis at 12 and 24 months from the baseline expressed as stable BASRI hip index.

2 Objectives

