3 METHODOLOGY

3.1 Summary of Study Design

This study is a non-interventional prospective observational cohort study. Patients participating after signing informed consent form will receive treatment and diagnostic procedures according to daily clinical practice conducted by his/her physician.

Visits during the study will include collection of data if already available. There are no procedures that are required as part of this study.

The study is to be conducted in multiple centers across Russia. AS patients with coxitis newly prescribed golimumab during the course of usual clinical care, will be enrolled and followed prospectively for 24 months with data collection at the approximate time points: baseline (pre-treatment) and consequent every 6 months. A time window of approximately \pm 6 weeks is envisaged for follow-up visits.

Product: MK-8259

Protocol/Amendment No.: 021

VEAP ID NO: 6189

Date: 15-January-2018

Patients will be screened and selected according to inclusion and exclusion criteria prior to enrollment. The study centers will maintain a list of all screened patients with the reasons for excluding patients being enrolled into the study.

Baseline data will be extracted from medical records (MR), if available at each treatment center. No additional interventional tests or medical procedures such as additional blood samples, X-ray or other technical investigations will be performed as a part of this study. If any data element is not available it will be reported as missing.

At baseline, data on age, gender, occupational status, AS and coxitis symptoms duration, concomitant disease, will be collected according to usual clinical practice.

C-reactive protein (CRP) is usually measured as part of the normal screening for patients prior to the initiation of a biologic agent in clinical practice. The results of this measurements will be collected. No additional blood withdrawals will be necessary for the study. CRP will be collected at baseline and at 6, 12, 18, 24 months if the measurements are available in regular clinical practice. Human leukocyte antigen B27 (HLA-B27) status (i.e. positive or negative) will be collected at baseline if available. Most AS patients will have this test performed as part of the diagnostic work-up in clinical practice.

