3.2 Study Population

All patients enrolled must be newly prescribed golimumab per the usual standard of care of the investigator.

In patients who have been prescribed these agents the moment of prescription is normally separated from the moment the agents are administered (e.g. administrative procedures, day-clinic visit to be scheduled, retrieval of the medicine at the pharmacist, etc.). Patients will be enrolled after the decision to treat with golimumab is made, but before the initiation of the newly prescribed medicine, i.e. patients must not have initiated treatment prior to the baseline data collection (enrollment).

Patient's data are to be collected after signing informed consent form and till the end of the study. If patient discontinues participation earlier, the data before discontinuation will be collected.

Patient can withdraw the informed consent form for any reason for any time. Investigator can decide to discontinue participation of patient for safety, lack of efficacy or any other reason.

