3.3 Inclusion Criteria

All inclusion and exclusion criteria will be reviewed by the investigator or qualified designee to ensure that the subject qualifies for the study.

Product: MK-8259

Protocol/Amendment No.: 021

VEAP ID NO: 6189

Date: 15-January-2018

All patients need to meet all of the following inclusion criteria:

1. Adult patients (>18 years of age) with definite AS (as per modified New York criteria)
2. Coxitis with BASRI-hip score 0-2
3. Newly prescribed golimumab according to usual clinical practice
4. Naïve to anti-TNFs or other biologic agents prior to initiation of golimumab as indicated by the patient's medical records
5. Patient is enrolled after the investigator's decision to treat with golimumab, but before initiation of treatment with golimumab
6. Patient was informed of the benefits and risks of golimumab as per normal practice using the product leaflet
7. Signed informed consent form

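### Section 1.2 reads a stable BASRI-hip as golimumab being radiologically effective, but an all-treated cohort with no reference and about 27 completers cannot attribute stability to the drug

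*Combined protocol and SAP*

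**What the plan says.** Section 1.2 (Rationale) says that "it can be expected that the TNF alpha inhibitor golimumab will be effective clinically and radiologically" and lists two expectations. The first is an improvement in BASFI at 12 months. The second, and the only radiological one, is that "there will be no structural progression of coxitis at 12 and 24 months from the baseline expressed as stable BASRI hip index". The same section faults earlier prospective work for stopping at 12 months, "when at least two years are recommended as a follow-up in AS to investigate the radiographic progression".

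On design, section 3.1 states: "This study is a non-interventional prospective observational cohort study". Section 3.2 adds: "All patients enrolled must be newly prescribed golimumab per the usual standard of care of the investigator". No comparison group or external benchmark is planned.

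Sections 2.2 and 8.1.3 list change in BASRI-hip at 12 and 24 months as a secondary measure, in neutral terms. Neither defines stability or sets a margin. Section 8.1 offers only paired difference tests for quantitative variables: the paired t-test, or the Wilcoxon signed rank test when normality or equal variances fail.

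Sections 8.2.1 and 8.2.2 name recruitment errors, dropout, departures from the label, data quality and missing data. Neither names the lack of a comparator or the natural course of hip damage.

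**The concern.** Section 1.2 is the only place that says how the radiographic result is to be read, and it reads no change as a drug effect. Improvement from baseline and absence of worsening are different kinds of evidence. Absence of worsening says something about a drug only if one knows how much worsening to expect without it, and the documents do not supply that.

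The two cited cohorts with BASRI-hip data do not fill the gap, because both were on TNF inhibitors. Of the 12-month etanercept cohort, section 1.1 reports: "In the whole population of patients BASRI-hip remained with no changes". The infliximab cohort, followed for about six years, was also unchanged, and section 1.1 says its authors assume, rather than show, that progression is inhibited.

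A report that followed section 1.2 could therefore credit golimumab with preventing structural damage on data that cannot separate this from the ordinary course of the disease. At 12 months it would do so over a period that the section itself treats as too short.

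**Working it through.** **1. The plan's own figures.** Section 8.3 sizes the study on BASFI only. With σ = 2.12 and d = 2.5, its formula with two-sided α = 5% and β/2 = 5% gives n = 12.99 × 2 × 2.12² / 2.5² = 18.7, close to the stated 18. For dropout, 39 × 0.70 = 27.3, which matches the stated 27 completers. No size, power or margin is given for BASRI-hip, so 27 is used below. Section 4.3.6 takes X-rays only when they are in the chart, so the number with films could be smaller.

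**2. Perfect stability.** With 0 progressors out of n, the exact two-sided 95% upper limit is 1 − 0.025^(1/n).

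- n = 27: 12.8%
- n = 18: 18.5%
- n = 39: 9.0%

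**3. What the paired test would miss.** Assume one BASRI-hip value per patient, and that every change is a worsening of one grade. With k progressors, the exact signed-rank p-value is 2 × 0.5^k. The asymptotic version, corrected for ties, has z = √k.

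- Exact: k = 5 gives p = 0.0625 and k = 6 gives p = 0.031, so six progressors are needed.
- Asymptotic: k = 3 gives p = 0.083 and k = 4 gives p = 0.046, so four are needed.

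Under the exact test, 5 of 27 (18.5%, exact 95% CI 6.3% to 38.1%) would count as no significant change. Section 8.1 does not say which version applies.

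**4. Chance of a stable-looking result when the drug does nothing.** The documents give no untreated rate, so the 24-month progression rate p is an assumption, shown over a range. The number of progressors is binomial(27, p). The chance of none is (1 − p)^27. The chance of non-significance is P(X ≤ 5) for the exact test and P(X ≤ 3) for the asymptotic test.

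| Assumed p | Expected progressors (27p) | No progressor | Non-significant, exact | Non-significant, asymptotic |
|---|---|---|---|---|
| 2% | 0.5 | 58% | 100% | 99.8% |
| 5% | 1.4 | 25% | 99.8% | 96% |
| 10% | 2.7 | 5.8% | 95% | 72% |
| 15% | 4.1 | 1.2% | 79% | 41% |
| 20% | 5.4 | 0.2% | 54% | 18% |
| 30% | 8.1 | <0.1% | 14% | 2% |

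**5. Duration.** Section 1.2 cites at least two years as the recommended follow-up for radiographic progression, and section 1.1 reports the same requirement from the infliximab cohort's authors. Section 1.2 then sets its structural expectation at 12 months as well as 24. The 24-month reading meets the stated standard and the 12-month reading does not.

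**The case against.** Section 1.2 states an expectation, not a success rule. Sections 2.2 and 8.1.3 speak only of change, and no section says that the report will claim structural benefit. The study is openly a single observational cohort, BASRI-hip is a secondary measure, and follow-up does run to 24 months. All of this stands, and it keeps the point modest. It does not remove the link that section 1.2 makes between stability and effectiveness, which no other section qualifies.

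Three stronger readings might be inferred, and the documents do not support them.

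- **That stability is likely whatever the drug does.** This needs an untreated rate. In the table, a non-significant result is the likely one at assumed rates up to about 10%, is no longer assured at 20% and is unlikely at 30%. Complete absence of progressors is more likely than not only at 2%. The long-run figure in section 1.1 (12–25% with a replaced hip after more than 30 years) does not settle it. At constant hazard, 1 − (1 − c)^(2/30) gives 0.8% to 1.9% per two years. If all replacements fell among the 24–36% with hip disease, c becomes 33% (12/36) to 69% (25/36), or 2.7% to 7.6% per two years. Either way this is an end-stage event, not a one-grade change.
- **That the entry rule, "Coxitis with BASRI-hip score 0-2", favours stability.** The scale runs to 4, so every patient has at least two grades in which to worsen. The infliximab cohort was stable from a higher mean grade, 2.50.
- **That the missing comparator makes stability more likely.** It makes stability impossible to attribute, which is a different matter.

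**Conclusion.** The point holds as one of interpretation. In a cohort where everyone is treated, with no untreated or historical reference and no definition of stable, a stable BASRI-hip cannot be taken as evidence that golimumab is radiologically effective. That conclusion needs no assumed rate.

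The size of the problem rests on 27 evaluable patients. No progressors would still be compatible with a true rate of up to 12.8%. At an assumed 10% rate with no drug effect, the paired test would be non-significant 72% to 95% of the time, depending on the version used. These test figures assume one value per patient and one-grade worsenings only. The conflict over 12 months follows from the text alone and is confined to the 12-month part of the expectation.

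The consequence is limited to what may be concluded from a secondary endpoint. The BASFI primary analysis is not affected.

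**What to change.** - **Section 1.2:** replace the second expectation with a statement that BASRI-hip change will be described as the number and proportion of patients worsening by at least one grade, with an exact 95% confidence interval. State that neither stability nor a non-significant change will be taken as evidence of radiological effectiveness, because there is no untreated reference.
- **Section 1.2:** name month 24 as the structural read-out and month 12 as descriptive.
- **Section 8.1.3:** carry the same summary into the analysis plan.
- **Section 8.2.2:** add the lack of a comparator and the unknown natural course of BASRI-hip to the limitations.

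Using earlier X-rays from the chart as a pre-treatment reference is not recommended. Entry requires a grade of 2 or below, and grades 3–4 and previous hip replacement are excluded, so patients who had already progressed further are missing and the pre-treatment change is truncated. Earlier films would also exist for only some patients.

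The cost is a few sentences and one simple table, with no added imaging, visits or patients. The downside is a weaker claim from a secondary endpoint.

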2.1 Primary Objective

- To evaluate change of functional impairment in AS patients with coxitis from baseline to 12 months of therapy with golimumab by BASFI in daily clinical practice

Product: MK-8259
Protocol/Amendment No.: 021
VEAP ID NO: 6189
Date: 15-January-2018

2.2 Secondary Objectives

- To evaluate change of functional impairment in AS patients with coxitis from baseline to 24 months of therapy with golimumab by BASFI in daily clinical practice
- To evaluate change of mobility impairment in AS patients with coxitis from baseline to 12 and 24 months of therapy with golimumab by BASMI in daily clinical practice
- To evaluate change of disease activity in AS patients with coxitis from baseline to 12 and 24 months of therapy with golimumab by ASDAS-CRP in daily clinical practice
- To evaluate change of BASRI-hip from baseline to 12 and 24 months of therapy with golimumab
To evaluate change of disease activity in AS patients with coxitis from baseline to 12 and 24 months of therapy with golimumab by BASDAI in daily clinical practice

2.3 Exploratory objectives

- To evaluate change of MRI signs of coxitis in AS from baseline to 12 months of therapy with golimumab in daily clinical practice
- To evaluate change of US signs of coxitis in AS from baseline to 12 months of therapy with golimumab
- To evaluate mean clinical scores (BASFI, BASMI, ASDAS-CRP, BASDAI) in subgroups of patients with or without MRI/US signs at baseline and their change at 12 months
- To evaluate occupational status of AS patients with coxitis at 12 and 24 months of therapy with golimumab in daily clinical practice

Data collected at 12 and 24 months are to be used for statistical analysis. But if these data is unavailable (e.g. due to early drop out before the final follow-up) data collected at 6 and 18 months are to be used according to analysis of last-observation-carried forward (LOCF) to minimize bias – section 8.2.1.

3 METHODOLOGY

3.1 Summary of Study Design

This study is a non-interventional prospective observational cohort study. Patients participating after signing informed consent form will receive treatment and diagnostic procedures according to daily clinical practice conducted by his/her physician.

Visits during the study will include collection of data if already available. There are no procedures that are required as part of this study.

The study is to be conducted in multiple centers across Russia. AS patients with coxitis newly prescribed golimumab during the course of usual clinical care, will be enrolled and followed prospectively for 24 months with data collection at the approximate time points: baseline (pre-treatment) and consequent every 6 months. A time window of approximately \pm 6 weeks is envisaged for follow-up visits.

Product: MK-8259

Protocol/Amendment No.: 021

VEAP ID NO: 6189

Date: 15-January-2018

Patients will be screened and selected according to inclusion and exclusion criteria prior to enrollment. The study centers will maintain a list of all screened patients with the reasons for excluding patients being enrolled into the study.

Baseline data will be extracted from medical records (MR), if available at each treatment center. No additional interventional tests or medical procedures such as additional blood samples, X-ray or other technical investigations will be performed as a part of this study. If any data element is not available it will be reported as missing.

At baseline, data on age, gender, occupational status, AS and coxitis symptoms duration, concomitant disease, will be collected according to usual clinical practice.

C-reactive protein (CRP) is usually measured as part of the normal screening for patients prior to the initiation of a biologic agent in clinical practice. The results of this measurements will be collected. No additional blood withdrawals will be necessary for the study. CRP will be collected at baseline and at 6, 12, 18, 24 months if the measurements are available in regular clinical practice. Human leukocyte antigen B27 (HLA-B27) status (i.e. positive or negative) will be collected at baseline if available. Most AS patients will have this test performed as part of the diagnostic work-up in clinical practice.

For disease activity the following instruments recommended for daily clinical practice will be used: BASFI, BASMI, ASDAS-CRP. These scores will be evaluated at baseline and at 6, 12, 18, 24 months.

Radiography of hip joint is used in clinical practice. BASRI hip will be collected at baseline and at 12, 24 months.

MRI (STIR (short tau inversion recovery) sequence and fat-saturated contrast-enhanced T1-weighted sequence) and ultrasonography (US) are used in clinical practice. Usually patients have either US or MRI, but sometimes physician may administer both radiology test if one of them is unsatisfactory as a diagnostic tool. Data of these tests will be collected at baseline and at 6, 12 months.

